- **Historical MGH control population:** Patients 21 years and older with a diagnosis of HF admitted to MGH cardiology services (Ellison 10 and 11) admitted in the year prior discharged home. Matched 1:2 based on age, sex, HFrEF(<40%), HFmEF(40-49%) HFpEF(≥50%), CAD, T2D, month admitted (minus 1y), number of prior 12mo hospital admissions.
- **Contemporaneous BWH control population:** Patients 21 years and older with a diagnosis of HF admitted to BWH cardiology services admitted during intervention study population enrollment and discharged home. Matched 1:2 based on age, sex, HFrEF(<40%), HFmEF(40-49%) HFpEF(≥50%), CAD, T2D, month admitted, number of prior 12mo hospital admissions.
- **Historical BWH control population:** Patients 21 years and older with a diagnosis of HF admitted to BWH cardiology services admitted in the year prior discharged home. Matched 1:2 based on age, sex, HFrEF(<40%), HFmEF(40-49%) HFpEF(≥50%), CAD, T2D, month admitted (minus 1y), number of prior 12mo hospital admissions.

Inclusion Criteria

- Adults (>21 years) admitted to MGH Cardiology services (Ellison 10 and 11) with a diagnosis of acute or chronic heart failure [HFrEF(<40%), HFmEF(40-49%) HFpEF(≥50%)] (or to BWH Cardiology services for BWH EHR-based controls)
- Has a smartphone or iPad and is willing to enter health metrics into DMP App and email willing to use for the study
- Access to the internet
- Established or with plan to establish primary cardiologist at MGH (or at BWH for BWH EHR-based controls)
- Discharged home or to self-care (with or without home services)

Exclusion Criteria

- Moderate or severe cognitive impairment
- Non-English-speaking
- Palliative management only (comfort measures)
- Does not own a smartphone or iPad (not considered for EHR-based controls)
- Incarcerated
- Enrolled in study with similar outcomes

Study Outcomes

Primary: To test the feasibility of implementing the AMAZE™ disease management platform intervention after in-patient heart failure hospitalization and patient perceived value of the AMAZE™ disease management platform. The feasibility will be measured using conversion rate (percent of patients approached who enroll on the disease management platform). The perceived value will be measured using the participants mHealth App Usability Questionnaire (MAUQ) score.

Exploratory: The following exploratory outcomes will be measured as follows:

1. Heart failure symptom changes using the Kansas City Cardiomyopathy Questionnaire (KCCQ).

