 - a. Heart failure symptoms will be measured as the changes in KCCQ scores between the 30 day and 60 day time-points.
2. Patient daily log compliance.
 - a. Daily log compliance will be measured after 60 days using the total number of days patient completes daily log in the AMAZE™ app out of total days patient is enrolled in the app.
3. Patient app usage.
 - a. Patient app usage will be measured as the number of days the patient engages (i.e. completes daily log, sends a message) with the app at least once a day during the study period.
4. Patient app messaging.
 - a. Patient app messaging will be measured as the number of messages sent by the patient during the 60 day study period.
5. Changes in hospital readmissions.
 - a. Hospital readmission rates in the enrolled study group will be compared to readmission rates in historical control groups.
6. Use of ancillary healthcare resources.
 - a. Rates ancillary healthcare resources (i.e. emergency room visits, urgent care visits, unexpected ambulatory care visits, cardiac rehab) in the enrolled study group will be compared to rates of usage in a historical control group.

Subject Enrollment

Overview

Approximately 70 patients will be enrolled in the study. Patients admitted to MGH cardiology will be screened by study staff for inclusion/exclusion criteria. Study staff will obtain approval to approach eligible patients by the inpatient clinical team. Approximately 2-days prior to discharge, suitable patients will be consented and onboarded with study staff, with the technical support available 24/7 via email or phone through BrightInsight, Inc.

Procedure for obtaining informed consent

We will use Mass General Brigham electronic resources to identify and screen patients for the eligibility criteria listed above. Our internal (MGH) data and analytics team developed an automated process to screen and extract a list of eligible admitted patients on Ellison 10/11 through Research Patient Data Registry (RDPR) and Enterprise Data Warehouse (EDW) (IRB Protocol # 2020P002432). The list will be sent to the study staff daily; study staff will perform chart review of participants on the list to confirm eligibility.

We will focus on patients with a diagnosis of heart failure, who speak and read English.

We will also use the attached study flyer to advertise the study to patients on inpatient floors, with nurse manager approval for the respective floors.

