We will create a database of potentially eligible subjects and contact their nurses to confirm eligibility and that they are suitable for the study. We will also verify that the nurse approves of a coordinator approaching their patient. A study coordinator will approach approved and eligible patients to introduce the study. The study coordinator will then review the consent form and study procedure and obtain written consent from the patient. Study coordinators will use an iPad to go over the consent form with the patient. The subject and the study coordinator will sign electronic copies of the consent form using Adobe eSign. Adobe and the iPad will be used whenever possible, but subjects also may be consented with a paper consent form. Subjects will be sent a copy of the consent form via email from Adobe, which automatically sends a pdf copy of the signed consent form to all parties, or they will be sent a scanned paper copy via the Partners send secure system. Subjects with any cognitive disability that prevents them from consenting for themselves will also prevent them from using the AMAZE application. Therefore, subjects who cannot consent for themselves will be excluded from the study. Staff will clearly explain that participation in the study is voluntary and the subject can choose to withdraw from the study at any time.

We will approach patients who are interested in joining the study but are transferred to other inpatient units for various reasons (procedures etc.) at their new location if permitted by their care team. We will verify that the patient is still interested in joining the study before consenting and onboarding them.

If we are unable to consent and/or onboard patients to the study while they are in the hospital, we will schedule a time to do so remotely using Partners Healthcare Enterprise Zoom once they have been discharged. In such cases, we will aim to enroll the patient within three days of being discharged from the hospital. With their consent, we will mail them their study devices: a blood pressure cuff and home scale. Patients can also refuse the study when talking to the research coordinator.

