Patients will be surveyed for baseline demographics and study outcomes. Medical history, including labs, procedures, and diagnoses will be collected from the medical record and recorded in REDCap

At consent, subjects will be surveyed for demographics that cannot be obtained from the medical record (See “Baseline Demographics” attachment).

Quality of life will be collected through the patient-facing AMAZE app (See “KCCQ” attachment). Patient satisfaction will be collected through MAUQ (attached) administered through the app. The app will also track patient medication adherence, and facilitate symptom, blood pressure, weight, and activity tracking.

At roughly 30 days from enrollment and again at 60 days from enrollment, a research coordinator will call the patient to collect 1) current cardiac medications and any changes to medication regimen and 2) hospitalizations, ED presentations, urgent care visits, primary care or cardiology visits, and cardiac rehab enrollment at institutions outside MGB. Research coordinators will review subject medical records to determine these events at MGB.

EHR data for the control populations (MGH and BWH) will be obtained from RPDR. We may also review medical records for these patients to collect/confirm EHR data.

Optional interviews

Two rounds of interviews regarding the user experience of the AMAZE app may be conducted over the course of the study. The interview questions ask about usability and helpfulness of the app, along with the option to give feedback about technical issues and features that could use improvement. These interviews

are optional and do not affect the participants' overall participation in the study. This is reflected in the consent form, with a section allocated to participants' choice of whether they would like to be contacted for these interviews or not.

Participants who consent to being contacted for the interviews will be selected based on engagement with the app. We will measure engagement by percentage of daily log compliance over the past seven days. Participants who fill out the daily log more than half the days in a week will be classified as "engaged with the app" and those who fill out the daily log less than half the days in a week will be categorized as "disengaged with the app."

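### Remote enrolment after discharge favours patients who escaped early readmission, and the EHR controls face no such condition, so exploratory comparisons 5a and 6a can lean modestly towards the platform

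*Combined protocol and SAP*

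**What the plan says.** The default route is in hospital: "Approximately 2-days prior to discharge, suitable patients will be consented and onboarded with study staff" (section III, Subject Enrollment, Overview). Under Procedure for obtaining informed consent there is a fallback for patients who could not be consented and/or onboarded before leaving: "we will schedule a time to do so remotely using Partners Healthcare Enterprise Zoom once they have been discharged", and in those cases "we will aim to enroll the patient within three days of being discharged from the hospital". Three days is a target, and no maximum is set.

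The participants' clock runs from enrolment: "At roughly 30 days from enrollment and again at 60 days from enrollment, a research coordinator will call the patient" (Data Collection and Surveys).

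Exploratory outcome 5a reads: "Hospital readmission rates in the enrolled study group will be compared to readmission rates in historical control groups". Outcome 6a treats ancillary care, including emergency room visits, in the same way. Neither states a time zero, a window length or an estimator.

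Controls come from the EHR. The historical sets are heart failure patients "admitted in the year prior discharged home"; the contemporaneous set is defined in parallel. They are "Matched 1:2 based on age, sex", ejection-fraction class, CAD, T2D, and, for the historical sets, "month admitted (minus 1y), number of prior 12mo hospital admissions". No matching variable concerns time since discharge, and no control has to be event-free to any day. The protocol does not say how it handles a patient who is readmitted before a scheduled remote session.

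**The concern.** Take a patient discharged before consent, with a video session booked for day 3, who is readmitted on day 2. That patient does not enter the study from the first discharge. If approached again and enrolled during the second stay, the second stay becomes the index admission, so the readmission is still not an event. An EHR control with the same course can qualify on the first admission, and on the plain reading of the control definition the day-2 return counts.

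Remote participants therefore bring guaranteed event-free time from the days just after discharge, and controls do not. This is immortal-time selection. It can lower the enrolled group's readmission and emergency-visit rates even if the platform does nothing. The matching variables describe history up to the index admission, so they cannot correct for what happens after discharge. Section II presents this pilot as preparation for a larger efficacy study, so a flattered readmission estimate could be carried forward.

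**Working it through.** **The plan's own figures.** None concerns readmission. The one power statement (section VI) is about KCCQ: n = 70, 0.40 SD, two-sided 5% (assumed, since alpha is not stated) gives 91.0%, so the claim of more than 80% holds. It has no bearing here.

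**Inputs from the documents.** 70 enrolled; 1:2 matching, so about 140 per control set; remote enrolment aimed at day 3.

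**Assumed inputs.** 60-day readmission 30%; true effect zero; remote share f of 25% or 50%; enrolment day L of 3, or 7 if the aim is missed; and either a constant hazard or 1% per day in the first week.

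**Step 1: early events.** The constant hazard is -ln(0.70)/60 = 0.00594 per day. The probability q of readmission by day L is 1 - exp(-0.00594 × L), or 1 - exp(-0.01 × L) with the higher early hazard.

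**Step 2: both groups counted to day 60 after discharge.** Controls have risk 0.30. A remote participant is event-free to day L, so has risk (0.30 - q)/(1 - q). The deficit per remote participant is 0.70 × q/(1 - q). Multiplying by f gives the group difference in percentage points:

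| L | Early hazard | q | Deficit per remote participant | f = 25% | f = 50% |
|---|---|---|---|---|---|
| 3 | constant | 1.77% | 1.26 | 0.31 | 0.63 |
| 3 | 1% per day | 2.96% | 2.13 | 0.53 | 1.07 |
| 7 | constant | 4.08% | 2.97 | 0.74 | 1.49 |
| 7 | 1% per day | 6.76% | 5.08 | 1.27 | 2.54 |

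At f = 50% (35 of 70 remote) the deficit is 0.44-0.75 events at day 3 and 1.04-1.78 at day 7, out of 70 × 0.30 = 21 expected. In relative terms that is about 2-4% and 5-8%.

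**Step 3: 60 days from each group's own origin** (enrolment for participants, discharge for controls).
- Constant hazard: a remote participant's 60-day risk is again 1 - exp(-0.00594 × 60) = 30%. The difference is zero.
- 1% per day in week one: the later hazard is (0.3567 - 0.07)/53 = 0.00541 per day. For L = 3 the risk is 1 - exp(-(4 × 0.01 + 56 × 0.00541)) = 29.0%, a deficit of 0.97 points per remote participant, or 0.49 at f = 50%. For L = 7 it is 1 - exp(-60 × 0.00541) = 27.7%, a deficit of 2.29 points, or 1.14 at f = 50%.

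**Step 4: wider range.** With 60-day readmission of 25-45% and a first-week hazard one to three times the later one, a common end day and L = 3 give 0.3-1.0 points at f = 25%, 0.5-2.1 at 50%, and 1.1-4.2 if everyone enrolled remotely. With L = 7 and f = 25% the range is 0.6-2.5.

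**Step 5: sampling error.** Treating the groups as independent, SE = sqrt(0.30 × 0.70 × (1/70 + 1/140)) = 6.7 points; it is 6.3-7.3 points at rates of 25-45%.

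**Step 6: aligned start.** If matched controls must also be readmission-free to day L and are counted from day L for the same window, both groups have the same conditional risk and the difference in this model is zero.

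These figures are for readmission. The size for emergency visits was not computed.

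**The case against.** Remote enrolment is a fallback, the comparison is exploratory in a single-arm feasibility pilot, and the bias is well below the sampling error. All of that stands, and it limits the weight of the point. It does not remove the bias, which has one direction and adds to whatever chance produces. The expected remote share is not stated either, so it cannot be taken as negligible.

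The fallback also covers patients consented in hospital and only onboarded later, who need not be lost if readmitted. This stands too, and it shrinks the affected subset.

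A patient enrolled at the second stay carries the first stay in the prior-admissions matching variable, and the protocol has no rule for choosing among a control's several admissions. Both are fair. That controls keep their early events is an inference from the absence of a time zero, not a stated rule. Even so, matching on history does not put the early readmission back as an event.

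Three stronger readings are tempting and are not supported:
- A reader might infer that equal window lengths never remove the bias. Under a constant hazard, with each group counted from its own origin, they remove it entirely.
- A reader might multiply q by the 35 remote participants and call the product (0.6-1.0 events at day 3, 1.4-2.4 at day 7) the bias. That overstates it, because the 35 are people who reached enrolment and still carry later risk.
- A reader might take 50% remote as expected. Nothing in the documents supports any particular share.

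**Conclusion.** The concern holds, at modest size. Remote participants are selected on being out of hospital until enrolment, controls are not, and no provision in the documents corrects this. The bias favours the platform when both groups are counted to a common day after discharge, or when risk is front-loaded; the plan fixes no origin or window and so rules out neither. At 30% readmission, no true effect and a common end day, it is about 0.3-0.5 points (25% remote) or 0.6-1.1 points (50% remote) for enrolment at day 3, and about 1.5-2.5 points for day 7 with 50% remote. The rate, hazard and remote share are all assumptions. A reader might infer that the pilot's main conclusions are compromised; they are not, because conversion rate and MAUQ score, the primary outcomes under Study Outcomes, do not use the controls.

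**What to change.** For outcomes 5a and 6a:

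- Record days from discharge to enrolment for every participant.
- Start each participant's risk time at the later of discharge and enrolment.
- Start each matched control's risk time on the same post-discharge day, choosing only among controls alive and not readmitted by that day.
- Use the same window length in both groups.
- Report how many approached patients were readmitted before a scheduled remote enrolment. Do not add them to the enrolled group's risk time, since they would fail the condition placed on controls.
- Add a sensitivity comparison limited to patients enrolled before discharge, with their matched controls.

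The cost is a little more matching work in each control set, and the loss of a few potential controls with very early readmission. No visit, consent step or element of care changes.

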The disease management platform (DMP) was co-developed by AstraZeneca (research & development center), Gaithersburg, Maryland, USA and BrightInsight, Inc., a Silicon Valley, CA-based health care technology company. AstraZeneca aims to improve patient engagement in their health, and enable convenient, effective support by allowing for messaging between study staff and patients based on a patient's progress with their care plan. The DMP consists of a patient held smartphone App, a clinician dashboard and a suite of clinical programs embedded into EPIC electronic medical record with configurable rules. The DMP App allows enrolled patients with heart failure to record relevant symptoms, biometrics, and medication adherence, as well as access their personal health information and stay connected with their care team. Patient-provided input via the daily log and monthly surveys are available for the healthcare team to view and assess. Patients can also access curated education links, view upcoming appointments, review trends in their recorded data, and send messages to the care team. The DMP App was developed by means of user-experience and design elements to ensure ease of use for all participants. The registration process is streamlined and will only take a few minutes to set up. In addition

to requiring a password-secured account for the DMP App, patients will be encouraged to add a passcode to their mobile device for additional security during the study.

AstraZeneca Content Procurement for in App Education Feature

AstraZeneca considers the Smartphone App as “patient-support” and not ‘commercial’ use. All of the HF App education links are trusted and reputable third-party medical sources. See below for a list of sources; all referenced sources are cited in the references section for web content that appears in the patient smartphone App. All content has been reviewed by AstraZeneca and MGH clinical teams with a proficiency in health literacy and patient education guidelines.

Referenced sources include:

- American Heart Association (www.heart.org)
- American College of Cardiology (www.cardiosmart.org)
- Heart Failure Society of America (www.hfsa.org)

Study staff and participants will have tech support via email ([contact]) tech support provided by BrightInsight, Inc. In addition to this participant support, additional support is provided to study staff by two identified IT professionals from LexTech.

Provider Dashboard

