The clinician dashboard is also produced by BrightInsight, Inc to work in conjunction with the DMP App for patients. AstraZeneca aims to strengthen existing clinical resources and reduce the burden and time spent on patient preparation and follow-ups by surfacing real-time insights to clinical teams and providing the tools to support patients easily and efficiently. The dashboard features secure, 2-way messaging to individuals and groups of patients, enabling efficient follow-up to answer patients’ questions and outreach to encourage engagement with the disease management platform. Clinicians can also reach out to patients through multi-channel communication methods, including email linked to Patient Gateway and a text chat feature in the App, to promote engagement and responses to surveys. The clinical team is alerted based on patients’ survey responses and engagement patterns, allowing them to identify risks, intervene early through supportive messaging, and reduce post-admission recovery complications. In summary the goals here is to provide, the real-time information about patients’ health status, combined with secure easy messaging with patients, which will enable an efficient, effective workflow for clinical teams to support patients through recovery and health maintenance.

III. RESEARCH DESIGN AND METHODS

Sample size: 70 post hospital admission at Massachusetts General Hospital (MGH), general cardiology with a diagnosis of heart failure with reduced ejection fraction (HFrEF), heart failure with moderate ejection fraction (HFmEF), or heart failure with preserved ejection fraction (HFpEF). Patients will be identified via an automated computer-based algorithm using information retrieved from electronic health records {Protocol #: 2020P002432}.

Inclusion/Exclusion Criteria for intervention study population

- **Intervention study population:** Patients 21 years and older with a diagnosis of heart failure [HFrEF(<40%), HFmEF(40-49%) HFpEF(≥50%)] admitted to MGH cardiology services (Ellison 10 and 11). Patients must have access to smartphone and email, be English speaking/reading and discharged home.

Non-recruited EHR-based control populations for the exploratory objectives for this single-arm interventional pilot:

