A blood pressure cuff and scale will be provided to all participants, along with instructions on how to use them.

Study Procedures

Study Staff and Nurse Navigator Role

A nurse navigator, with experience working with patients and cardiologists on cardiovascular disease prevention, management, and rehabilitation will also work with patients through the dashboard to promote adherence to care plans and provide support and encouragement throughout preparation and recovery. The nurse navigator will partner with research staff and the cardiology care team to ensure a seamless support system for patients. The nurse is a MGH staff who is a trained in coaching, patient

support, engagement, and encouragement. The nurse navigator builds a supportive, mentor-like partnership with the patient, fosters encouragement, goal setting and accountability to maximize engagement. The nurse sends encouraging messages and addresses patients' non-clinical and clinical needs, when possible. The nurse promotes and assists patients with adherence to completing the tasks in their DMP App including engagement in heart failure-related education, completing a daily log, monthly surveys and care team communication.

The nurse navigator partners with patients and the clinical team via the DMP dashboard messaging system. The nurse navigator facilitates triage of clinical needs and will act as a liaison between patients and the care team to bridge the gap and improve patient navigation, familiarity and stability in a complex medical system. Outgoing telephone calls to patients will be documented in EPIC as a Telephone Encounter, calls will be routed to a study physician for review and to clinical physicians when longitudinal care questions or follow-up may be indicated. The nurse operates under the supervision of MGH cardiology team of licensed physicians and nurse practitioners, and all patient communication adheres to structured protocols and guidelines set forth by MGH clinical leadership.

Clinical providers will be able to monitor the subjects' App entries within EPIC via the provider dashboard. Study staff will be able to access the Provider dashboard, the clinician messaging function will be used for study communications and clinical care team communications for Heart Failure; any clinical questions needing MD or NP expertise will be directed to the patient's cardiology team by the nurse navigator for review and feedback.

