Heart Rate greater than	>100 bpm	once
Heart Rate less than	<60 bpm	once
Log Compliance	< 1 entry	Over 5 days

Participants will be asked and encouraged to enter information into the App daily. Information that will be entered into the App include:

- Physical well-being – How are you feeling today? [bad, okay, good]
- Medications – Have you taken all of your medications for heart failure today? [yes, no]
 - Medication list will be auto populated in the DMP App as part of the EPIC integration process. The list the patient can see in the HF DMP App will mimic what is in Patient Gateway.
- Symptoms – What symptoms do you have today? [cough, difficulty sleeping flat, dizziness, fatigue, leg/ankle/foot swelling, loss of appetite, shortness of breath, weakness, none of these]
- Activity – How active were you today? [Mild - none or <5 minutes, Moderate – 6 to >30minutes]
- Biometrics – weight, blood pressure, heart rate
- Kansas City Cardiomyopathy Questionnaire (see attachment) at 30-and 60-days

Participants without access to a home scale and/or blood pressure monitor to measure weight and blood pressure will be provided with device(s) purchased by the research study fund. Participants receiving a device will be able to keep the device(s) once the study has ended.

Participant Education Objectives and Outline

The educational components of this pilot study aim to provide key facts to individuals (and family) diagnosed with heart failure, to aide in their ability to stay active and well. Our education will focus on medication adherence, symptom recognition and management, communicating to your care team and lifestyle habits that can contribute to healthy living.

1. Participants will be able to identify the most common symptoms related to heart failure and recognize the importance of sharing specific changes in these symptoms to their doctor or care team or nurse navigator; to help with management and optimization of their disease.
2. Participants will become familiar with the names of their heart failure medications, maintain an accurate list of the medications and doses and co-create actions to ensure they take these medications daily.
3. Participants will gain knowledge about safe, regular activity and food choices that can impact their weight and heart failure symptoms.

Data Collection and Surveys

See “Study Schematic” Section for a visual overview of the study.

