Summary metrics from recruitment data will be shared with the sponsor, including the percentage who joined the study out of those eligible, reasons patients did not join the study, and the demographics of eligible patients. Summary metrics and study results will be shared with the sponsor, but the individual level subject data collected in REDCap will not. Additionally, aggregated summary information about the controls used in the study will be shared with the sponsor, but individual-level control data will not be shared.

Data collected by the AMAZE™ app from the patient's medical record: their demographics including zip code, appointment information including dates and locations of appointments, PCP information, conditions and the dates associated with them, and their medications will be sent to the sponsor by BrightInsight. Additionally, information collected by the app directly from the app: user metrics, message information (not the content of the message), survey responses (KCCQ and MAUQ), and other tracked information: medication adherence, and facilitate symptom, blood pressure, weight, and activity tracking, will all be sent to the sponsor by BrightInsight. This information is included in the document "BrightInsight Data" attached.

V. EXPECTED BENEFITS

We hope that this study will help us better understand and improve heart failure management remotely via enhanced access to care and communication between the patient and the care team, using the patient App and provider dashboard. During the time between hospital discharge and a heart failure follow-up appointment, it is critical for patients to comply with the diet and exercise advice given to them and take their medications as prescribed. This study will help us better understand patient compliance with these activities when they leave the hospital, and guide future studies on patient mobile health application usage. We hope this study will also lead to development of better strategies to coordinate care between the time of discharge, the next follow up appointment and beyond. Potential benefits to subjects from this

study might include increased medication adherence and better adherence to health behaviors associated with decreased heart failure disease risk.

VI. POWER ANALYSIS

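### The primary MAUQ score is collected only inside the app it rates, so disengaged patients may be under-represented and the score may be too favourable

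*Combined protocol and SAP*

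**What the plan says.** Study Outcomes (section III) names two primary measures: conversion rate for feasibility, and the MAUQ for perceived value: "The perceived value will be measured using the participants mHealth App Usability Questionnaire (MAUQ) score". Data Collection and Surveys gives the route: "Patient satisfaction will be collected through MAUQ (attached) administered through the app". Section IV (Sponsor) again lists "survey responses (KCCQ and MAUQ" among the data that the app collects.

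The same part of section III describes calls at about 30 and 60 days, in which "a research coordinator will call the patient to collect 1) current cardiac medications and any changes to medication regimen", together with healthcare use outside the hospital network. The MAUQ is not on that list.

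Under Study Closeout and Post Study Follow-up, patients may stop using the app at any time, and lack of engagement is not a reason for staff to withdraw them. App access ends at withdrawal or completion, and the 60-day call includes a reminder to delete the app.

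Some text works the other way. Patient Smartphone App says "Patient-provided input via the daily log and monthly surveys are available for the healthcare team to view and assess". The nurse navigator helps patients with "completing a daily log, monthly surveys and care team communication". Provider Dashboard describes outreach by email and in-app chat "to promote engagement and responses to surveys". The KCCQ has dates, "Kansas City Cardiomyopathy Questionnaire (see attachment) at 30-and 60-days", but the visible text gives none for the MAUQ. The study schematic and the MAUQ attachment, which may give them, are not available here.

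**The concern.** A patient can return the rating only by opening the product being rated. Someone who gives up on the app remains in the enrolled group but no longer uses the one route to a score. The protocol expects such patients: it sets a log-compliance alert, defines disengagement for the optional interviews, and reserves interview places for disengaged participants. It gives them no off-app route for the primary measure.

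Disengaged patients plausibly rate the app lower, so the likely error is a score that is too favourable. That direction is an inference; the documents hold no data on it. The pilot is presented as the step before a large multi-center efficacy study, so it matters whether perceived value describes all of the roughly 70 enrolled or only those who kept using the app. The visible text plans neither a MAUQ response rate nor a comparison of responders with non-responders, so a reader could not tell which.

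**Working it through.** **The plan's own figure.** The plan has no computed figure for the MAUQ. Its one power statement (section VI) concerns the KCCQ, which that section calls the primary outcome; the present point follows Specific Aim 1 and Study Outcomes, where the MAUQ is primary. The KCCQ figure reproduces: a paired t-test with n = 70, 0.40 SD and two-sided 0.05 (test and alpha assumed) gives 91.0% power, consistent with more than 80%. It has no bearing on the MAUQ route.

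**Inputs.** N = 70 (section III). Everything else is assumed: f is the share without a MAUQ score, and d is the amount in SD by which non-responders would have scored lower, on a scale where higher is more favourable.

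**Bias against precision.** Bias of the responders' mean = f × d. The 95% confidence half-width in SD units = t(0.975, n−1)/√n, with n = 70 × (1−f).

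| f | n | Half-width | Bias, d = 0.5 | Bias, d = 1 |
|---|---|---|---|---|
| 10% | 63 | 0.252 | 0.05 | 0.10 |
| 20% | 56 | 0.268 | 0.10 | 0.20 |
| 30% | 49 | 0.287 | 0.15 | 0.30 |
| 40% | 42 | 0.312 | 0.20 | 0.40 |

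Over 1 to 65 non-responders, with d = 1 the bias first exceeds the half-width at 20 of 70 (20/70 = 0.286 against 0.284). With d = 0.5 it never does; the largest ratio of bias to half-width is 0.78.

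**Partial completion among the disengaged.** Suppose 30% disengage, and 90% of engaged and 20% of disengaged patients complete the MAUQ. Completion is 0.7 × 0.9 + 0.3 × 0.2 = 0.69. Disengaged patients are 0.06/0.69 = 8.7% of responders, and the bias is (0.30 − 0.087) = 0.21 times the gap between engaged and disengaged. If half of the disengaged complete it, completion is 0.78, their share is 0.15/0.78 = 19.2%, and the bias is 0.11 times the gap.

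**Non-response for other reasons.** If half of the non-response is illness, readmission or death with no score gap, bias = f × d/2, and the range becomes 0.025–0.20 SD. The 1 SD case then equals the 0.5 SD column, so the bias no longer exceeds the half-width anywhere.

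**What a second route would recover.** Suppose half of the non-responders are scored.

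- Representative half: remaining bias = f·d − (f·d/2)/(1 − f/2).
- Selective half (recovered patients carry gap d/2, the rest 1.5d): f·d − (f·d/4)/(1 − f/2).
- Selective half, with phone answers 0.25 SD more favourable: add 0.25 × (f/2)/(1 − f/2).

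| Case | No second route | Representative half | Selective half | Selective half, phone shift |
|---|---|---|---|---|
| f = 20%, d = 1 | 0.20 | 0.089 | 0.144 | 0.172 |
| f = 40%, d = 1 | 0.40 | 0.150 | 0.275 | 0.338 |
| f = 20%, d = 0.5 | 0.10 | 0.044 | 0.072 | 0.100 |

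The first formula applies equally if an earlier monthly MAUQ has already scored a representative half of later non-responders. In the least favourable cell (last row, last column) the phone route gains nothing.

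**The case against.** The strongest reply is that timing decides the matter and timing cannot be seen. If the MAUQ is one of the monthly in-app surveys, many later quitters would already have a day-30 score. That stands as a limit on the size, and the missing date cannot be held against the plan while the schematic is unavailable. For the same reason, deactivation and the reminder to delete the app matter only if the MAUQ is still outstanding at the end.

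Second, the plan targets falling engagement. Staff are alerted when there is less than one log entry over 5 days, patients can be reached by email as well as in the app, and the nurse navigator helps with surveys. This should raise completion. But these are prompts to return to the app, not another way to answer, and care-team messages sent through the app are read by opening it.

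Third, every bias input is assumed, the bias exceeds the half-width only with a 1 SD gap and at least 20 of 70 missing, and this disappears if half of the missing scores have no gap. That is correct. So is the remark that no threshold is visible, that conversion rate is unaffected, and that planned app-use outcomes would show disengagement beside the score. What those outcomes would not show is whether the people who supplied the MAUQ resemble those who did not.

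Fourth, a phone route brings a mode effect that cannot be separated from non-response, because only patients without an in-app score would use it. That also stands, and is why the two sets of scores should be shown separately.

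**Conclusion.** The concern holds. In the visible text a primary measure has a single patient route, through the app under evaluation, while patients who leave the app remain enrolled. Under assumed non-response of 10–40% and a gap of 0.5–1 SD, the mean is too high by 0.05–0.40 SD; with half of the non-response unrelated to dissatisfaction, by 0.025–0.20 SD. The bias is zero if completion does not depend on engagement or if there is no gap. The direction is plausible but undocumented, and the size is unknown. No stated figure or pass/fail decision is shown to be wrong. The consequence is one of interpretation: part of the primary result may describe continuing users. The change should be made because it is cheap, and confidence in the point is moderate.

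**What to change.** 1. State the MAUQ time-point or time-points in the text if the schematic does not already do so.
2. At the existing 60-day call, before the reminder to delete the app, offer the MAUQ to anyone who has not completed it in the app; at withdrawal, offer it if the patient agrees. It can be given by phone or by an emailed REDCap link. The clinician survey already uses such links, and eligibility already requires an email address. Record the mode.
3. Report the response rate over all enrolled, known reasons for non-response, and the score for in-app completers alone and for all completers.
4. Compare responders with non-responders on daily-log compliance, app-use days and messages sent. Show the mean with disengaged non-responders set 0.5 and 1 SD lower, keeping death and readmission separate from disengagement.

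Items 3 and 4 need no new measurements beyond the MAUQ itself and any known reasons for non-response. Item 2 needs a wording change and probably a few minutes on a scheduled call; the questionnaire's length is in an attachment not seen here, so that time is an assumption. Usability questions are already planned on these calls for up to 10 interviewees. The link would be a new patient-facing use of REDCap.

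There would be two data routes. App responses go to the sponsor, but individual REDCap data do not. MGH also receives the app data, so it can combine the two and share the summary. A phone-mode effect should be stated as a limitation; an emailed link avoids answering to a coordinator but leaves mode confounded with non-response.
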